5.3.2. Estimand

The first key secondary estimand to be estimated in the study, is defined by the following -

- Population: FAS (i.e., all randomized participants with HF who either have HF_rEF or HF_pEF, regardless of T2DM status with at least one dose of study intervention and at least 1 post-baseline KCCQ measurement)
- Treatment: canagliflozin 100 mg or placebo

- Variable: change from baseline to Week 12 in the daily step count averaged over 2-week intervals
- Intercurrent event: treatment discontinuations (either due to AE or other reasons) or treatment switching or temporary disruption in daily activity; use treatment policy strategy to address intercurrent events (i.e., use all available measurements collected during study, regardless of the occurrence of the intercurrent event); events of “loss to follow up” or “study withdrawal” or “death” are not considered intercurrent events but rather missing data.
- Population-level summary: difference in mean change from baseline to Week 12 in the daily step count averaged over 2-week intervals (i.e., difference is based on subtracting the average of daily step count for Week 11 and Week 12 from the baseline 14-day average daily step count) between two randomized groups.

5.3.3. Analysis Methods

Daily step counts and daily floors climbed data at baseline will be presented as 14-day averages of daily counts starting with the first dose date and ending with Day 14 during the double-blind treatment period. This method of averaging will continue until end of Month 9 (Day 252) or, until the time of end of study (EOS) observation is available.

The above two key secondary endpoints will be analyzed in two ways –

- 1) following the same approach as employed for the primary effectiveness endpoint (i.e. using an MMRM model adjusting for baseline covariates such as treatment, stratification factor and baseline average step count).
- 2) by calculating mean change from baseline to Week 12 in daily step counts using the corresponding 14-day averages at baseline and Week 12 respectively. That is, the mean difference in the 14-day averages in daily step counts or daily floors climbed is calculated for each randomized intervention group and difference in mean changes between the 2 randomized intervention groups will be compared using a 2-sided t-test.

As stated in Section 1.3, the first key secondary endpoint of daily step count will be tested once the primary endpoint is shown to be statistically significant at 5% significance level.

Other secondary endpoints refer to changes in the KCCQ individual domain scores (physical limitation, quality of life), and the KCCQ clinical summary and overall summary scores from baseline to Week 12. The individual KCCQ domain scores as well as the summary scores will be produced at each time point (based on the KCCQ algorithm) with changes from baseline calculated at each specified post-baseline time point. For these endpoints, an MMRM model (like that specified for the analysis of the primary endpoint) will be employed to summarize changes over time from baseline to Week 12. Hypotheses related to these domains will be independently tested at 5% without any control for overall type I error rate.

5.4. Exploratory Variables

5.4.1. Definition

The exploratory endpoints are the following:

-
- mean PGIC scores over time
 - changes in PGI-S scores from baseline to Week 12
 - change in HRU and health economics data
 - number of outpatient intravenous therapies, ED visits, and hospitalizations
 - time to first hospitalization/readmission for heart failure
 - time to first hospitalization/readmission for other events
 - time to death

5.4.2. Analysis Methods

The exploratory endpoints listed below will be presented using descriptive statistics at each time point measurements are taken. Where specified, 95% confidence intervals (CIs) and p-values will be presented but no multiplicity adjustment will be made. Analyses of mean changes from baseline to Week 12 and month 9 (Day 252) respectively will be conducted, as described below.

- Appendix 6: Patient Global Impression of Change (PGIC) is a validated generic tool for assessment of overall change in the severity of illness following treatment. Participants rate how they feel now compared with how they felt before receiving study intervention on a 7-point scale where 1 is “Very much improved” and 7 is “Very much worse”. A mean \pm SD PGIC score for each time point will be calculated by randomized intervention group. Distribution of PGIC score at Week 12 will also be presented. Based on the PGIC symmetric scale, a dichotomous scale of “Yes” or “No” will be derived. A favorable change is score of 1-3 = ‘Yes’, which means there is significant improvement with the study intervention. If the response is 4-7 = ‘No’, it is considered no significant change. Change in the KCCQ-TSS from baseline to Week 12 by PGIC response at Week 12 will be summarized by treatment group, and, also graphically displayed (i.e., x-axis will display categories of PGIC response at Week 12 and y-axis will display mean change scores from baseline to Week 12 in KCCQ-TSS by treatment group).
- Distribution of participants in PGI-S (see [Appendix 7: Patient Global Impression of Severity \(PGI-S\)](#)) response categories will be summarized by randomized intervention group at baseline and by Week 12. Mean change in PGI-S score between baseline and Week 12 will be summarized by randomized group. Change in the KCCQ-TSS from baseline to Week 12 by PGI-S response at Week 12 will be summarized.
- For daily activity measured by daily step counts, total active days (defined as Fitbit recorded ≥ 100 steps) and percent of active days to total days spent in the study analysis period will be summarized for each intervention group using mean and SD. Level of daily activity will also be described using categories of total step counts per day – 1) < 3000 steps per day (low activity/sedentary), 2) 3000-5999 (moderate activity), and 3) ≥ 6000 steps per day (high activity). Associations between daily step count (categorized into activity levels) and baseline characteristics (eg, age, sex, race, T2DM status, EF type, etc.) will be examined using a 1-way ANOVA for continuous data values and the Fisher exact test for categorical data.
- Correlation between total step counts per day and clinical events (eg, # of outpatient intravenous therapies, # ED visits, # hospitalizations, etc.) will be described for the double-

blind treatment period and total study duration separately. Relationships between change in step counts/floors climbed and incidence of reported clinical outcomes and PRO measures will be examined at the end of the double-blind treatment period and end of study separately.

- Daily floors climbed will be summarized by each intervention group for the double-blind treatment period and over the entire study duration separately.
- Descriptive statistics (ie, N, mean, SD, minimum and maximum) will be presented for total HRU and health economics data for each intervention group separately for the double-blind treatment period and the observational (no intervention) period. HRUs and health economics data typically include information regarding participants using health services for managing any clinical events/illnesses, hospitalizations/ED visits, surgeries, medication issues/prescription changes, and costs incurred.
- Descriptive statistics will be presented for participant's satisfaction with his/her experience with the virtual design at the end of the study.
- Using data from claims, the number of outpatient intravenous therapies, ED visits, and hospitalizations by each intervention group will be summarized. These summaries will include descriptive statistics.
- Using data from the claims and data on deaths, time to first hospitalization/readmission for heart failure, time to first hospitalization/readmission for other events, and time to death will each be analyzed using a Cox's regression model both for the double-blind treatment period and the entire study duration and include terms for study intervention and stratification factor (HFrEF/HFpEF). Hazard ratios, corresponding 95% CIs, and associated p-values will be presented. Distribution of the times to first hospitalization/readmission for HF, time to first hospitalization/readmission for other events, and time to death will be displayed with Kaplan-Meier curves. Participants who do not experience any such events of interest during the study analysis period will be considered 'censored' in these analyses.

No adjustment for multiplicity will be performed for the exploratory analyses listed above.

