Daily activity measurements via the Fitbit device will be collected continuously from the time study started (ie, when both the smartphone and the Fitbit are linked by a participant). Fitbit daily activity data will be aggregated into averages over 2-week intervals starting with a baseline period (ie, Baseline = average of Study Day 1 to Study Day 14) and similarly over the entire post-baseline study duration for each participant. This is to allow capturing a robust length of physical activity for each participant using the Fitbit device and minimizing variability associated with measurements in shorter time spans. The end-of-treatment (EOT) average value of the step count will be the average of the last 14 days prior to the last dose of study intervention, regardless of when the last dose is taken.

Claims data will be extracted as access to participant-level information becomes available. This will include clinical outcomes (including hospitalizations for HF and/or other reasons) coded using International Statistical Classification of Diseases and Related Health Problems (ICD)-9 and ICD-10 as appropriate.

Time windows will not be applied to summarize the safety data collected through claims. Self-reported safety data will be summarized through Week 12 (Day 87).

Table 1 presents the time windows and the target days for each time of measurement defined in the protocol.

Table 1: Measurement Windows

Parameter	Time Interval (label on output)	Time Interval (Day)*	Target Time Point (Day)
KCCQ (and its individual domains); PGIC and PGI-S; participant satisfaction survey	Screening/Baseline	-21 to <1	1
	Week 2	11 to 17	14
	Week 4	25 to 31	28
	Week 6	39 to 45	42
	Week 12	81 to 87	84
	Month 6	161 to 175	168
	Month 9	245 to 259	252
Daily Step Count / Daily Floors Climbed **	Baseline to Week 2	1 to 14	
	Week 3 & Week 4	15 to 28	
	Week 5 & Week 6	29 to 42	
	Week 7 & Week 8	43 to 56	

Parameter	Time Interval (label on output)	Time Interval (Day)*	Target Time Point (Day)
	Week 9 & Week 10	57 to 70	
	Week 11 & Week 12	71 to 84	
	
	Week 35 & Week 36	238 to 252	

*Relative to Study Day 1

** Measurements over a 2-week interval with ≥ 100 daily steps to allow capture of physical activity

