Missing and incomplete data in KCCQ PRO measure may be of 2 types: missing at the form-level and at the item-level. Form-level missing data refers to a participant missing an entire PRO assessment for a scheduled time point. If not otherwise specified, analyses will be conducted on all available data and form-level missing data will not be imputed. For the KCCQ, derivation of individual domain scores in the presence of missing item-level responses will follow algorithms specified in the KCCQ manual. PRA will calculate baseline KCCQ overall summary score based on the KCCQ app and include in the analysis database. For calculation of all other KCCQ domain scores (including the KCCQ-TSS) at baseline and at all post-randomization time points, scoring instructions available per the KCCQ manual with Janssen will be followed (see Appendix 8). For the PGIC and PGI-S measures, a single imputation (ie, last observed scores carried forward) for missing post-baseline scores will be used as a conservative rule. Vertical file formats will be prepared for all PRO data, reading one record per patient for each measurement time (ie, baseline, Weeks 2, 4, 6, and 12, and Months 6 and 9, respectively).

Fitbit Data - Clinical (Activity) Measures

Data from the Fitbit device pertaining to the daily total step counts and daily total floors climbed will be aggregated over 2-week intervals for the entire study duration (see [Table 1](#)). Due to the general sedentary nature of HF patients, Fitbit recorded <100 steps taken in a day will not be

considered in the calculation of averages for daily step counts . If missing >7 days (50%) in a 2-week interval, the corresponding 2-week interval average will be set to missing.

In case of premature discontinuation of the study intervention, the average of the last non-missing 14-day window prior to the last dose of study intervention will always be used as an EOT value. If the EOT value corresponding to the period (EOT-14, EOT-1) is missing (not valid), the EOT period will be rolled back by one day, ie, (EOT-15, EOT-2), (EOT-16, EOT-3), until a non-missing (valid) value is available. This corresponds to a last observation carried forward (LOCF) up to Week 12/EOT approach. If no post-baseline daily activity data have been collected for at least 7 days over a 14-day time window, no EOT value will be computed, and the post-baseline value will be set to missing.

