5.3. Secondary Endpoints

5.3.1. Definition

The first key secondary effectiveness endpoint is change in the daily step count from baseline to Week 12 averaged over two-week intervals. Even though evidence of a meaningful change in daily step count in chronic HF patients via Fitbit device is not readily available, there are several studies that have conducted six-minute walk tests (6MWT) among HF patients in general and examined a minimum clinically important difference in daily step counts under different conditions. A change of 30 meters¹⁰ (approximately 1000 steps) may be considered in the present study to be of clinical interest to benchmark the expected mean change in daily step count in this study over the double-blind treatment period. This expected mean change in daily step count will also be examined in relation to variables such as PRO measures (as anchors) and clinical outcomes to better characterize treatment effect on daily activity.

As HF patients are generally not consistent in their daily walk patterns, there will be variations in levels of their daily activity (whether it is a weekday or a weekend) as well as variability in the total wear time of the Fitbit device. As a rule, we will consider Fitbit recorded ≥ 100 steps¹³ taken in a day in the calculations of averages. This will ensure capturing any meaningful level of physical activity while avoiding even smaller variations in daily steps taken by a participant wearing a Fitbit device. For each participant, baseline daily step count will be calculated by averaging daily step counts from Study Day 1 through Study Day 14. All subsequent post-baseline daily step count data will also be averaged in 2-week intervals. The change from baseline to Week 12 in daily step count will be based on subtracting the average of daily step count for Week 11 and Week 12 from the baseline average for each participant. Additionally, daily step count data will be averaged in 3-, 5- and 7-day (1-week) intervals at baseline and throughout the treatment period respectively and corresponding changes from baseline will be calculated.

The variable daily floors climbed will also be aggregated in a similar fashion.

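### SAP 5.4.2: percent of active days is taken over all days in the analysis period, so the by-arm summary confounds Fitbit wear with activity

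*SAP*

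**What the plan says.** The daily-activity bullet of SAP 5.4.2 plans to summarise "total active days (defined as Fitbit recorded" 100 steps or more), and then "percent of active days to total days spent in the study analysis period will be summarized for each intervention group using mean and SD". It does not say how a day without Fitbit data is counted. The same bullet sorts daily totals into three levels (below 3000, 3000 to 5999, and 6000 or more), the lowest being labelled "steps per day (low activity/sedentary").

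Elsewhere the plan expects gaps in the Fitbit data and handles them differently:

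- SAP 5.3.1 acknowledges "variability in the total wear time of the Fitbit device". Its only response is the 100-step cut, which removes days from the averages and is justified thus: "This will ensure capturing any meaningful level of physical activity while avoiding even smaller variations in daily steps".
- SAP 5.1.2 has a missing-day rule for the step averages: "If missing >7 days (50%) in a 2-week interval, the corresponding 2-week interval average will be set to missing". It is not stated to apply to the percent of active days.
- SAP 2.1 starts activity collection when phone and Fitbit are linked, whereas SAP 2.5 counts study days from the first dose.
- Protocol 4.1 provides for monthly central monitoring that includes detecting non-use of the device, with follow-up contact.

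Neither document defines a valid wear day. SAP 2 analyses exploratory endpoints over both the 12-week period and the full 9 months.

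**The concern.** A day can enter the numerator only if the device was worn and its data reached the study database. It enters the denominator simply because the participant was in the analysis period. Unworn and unsynced days therefore score as not active, although the step averages treat days without data as missing.

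If the arms differ in wear, the table will show a difference that looks like activity. The possibility is more open in the 9-month summary, because participants learn their allocation after completing the 3-month treatment period (Protocol 4.1, Participant Unblinding) and wear could then differ by arm for reasons other than activity. The documents offer no evidence that it will. The reverse error is also possible: a wear difference can hide, or change the sign of, a real difference in activity.

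**Working it through.** The documents state no figure for this summary, so there is none to reproduce.

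**Inputs from the SAP.** Active day: at least 100 recorded steps (5.4.2). Denominator: all days in the analysis period (5.4.2). Length of the double-blind period: 84 days (Table 1 and Appendix 3).

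**Inputs assumed.** Let w be the share of days with a usable Fitbit record and p the probability that such a day reaches 100 steps. Neither is in the documents. For the arm comparisons I took w from 0.75 to 0.85 and p from 0.70 to 0.98.

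**Formula.** With w and p independent across participants:

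- expected percentage, SAP denominator = 100 × w × p
- expected percentage, denominator limited to days with data = 100 × p

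**Equal activity, unequal wear (85% versus 75%).** The false difference is 100 × p × (0.85 − 0.75).

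| p, both arms | SAP definition | Difference | Days-with-data denominator |
|---|---|---|---|
| 0.98 | 83.3% vs 73.5% | 9.8 points | 98% vs 98% |
| 0.90 | 76.5% vs 67.5% | 9.0 points | 90% vs 90% |
| 0.70 | 59.5% vs 52.5% | 7.0 points | 70% vs 70% |

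The count of active days has the same problem. Over 84 days at p = 0.98 it is 84 × 0.85 × 0.98 = 70.0 against 84 × 0.75 × 0.98 = 61.7.

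**Equal wear (80%), unequal activity (p = 0.98 versus 0.90).** 0.80 × 0.98 = 78.4% against 0.80 × 0.90 = 72.0%, a difference of 6.4 points. The statistic does respond to activity.

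**Both unequal, in opposite directions.** With p = 0.98 and w = 0.75 in one arm, and p = 0.90 and w = 0.85 in the other, the result is 73.5% against 76.5%. The more active arm looks less active.

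**How much of the spread between participants is wear?** I simulated independent beta-distributed w and p, with w having mean 0.90 and SD 0.08, or mean 0.80 and SD 0.15. The share of variance explained by wear was:

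| Mean p (SD) | Share explained by wear |
|---|---|
| 0.98 (0.02) | 95–99% |
| 0.95 (0.05) | 74–92% |
| 0.90 (0.10) | 39–73% |
| 0.80 (0.15) | 18–49% |

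Wear dominates only if nearly every worn day passes 100 steps. That is plausible, because 100 is 1/30 of the SAP's own 3000-step limit for its lowest category, but the documents do not establish it.

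**The case against.** The strongest reply is that this is a descriptive mean and SD with no test attached, that it is not listed among the exploratory endpoints in SAP 5.4.1, and that nothing else in the plan depends on it. That stands, and it sets the weight of the point. Central monitoring for non-use may also limit gaps, although it does not change how the remaining gaps are counted.

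Second, a days-with-data percentage is not the truth either. Unworn days may be days of illness or a hospital stay. A participant with 7 of 14 days recorded, all active, is 50% active on the SAP definition and 100% on recorded days, and the real value is unknown. This also stands. It is a reason to show wear and activity side by side and not merely to swap denominators. It also argues against defining a valid day by non-zero steps, which would discard genuine zero-step days.

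Four stronger readings are tempting, and the documents do not support them:

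- *The percentage measures wear rather than activity.* It is the product of the two, and no figure in the documents shows which dominates.
- *Days before the Fitbit is linked count as inactive.* SAP 2.1 ties the start of activity collection to linking, while SAP 2.5 counts from first dose. The text is ambiguous.
- *Unworn days are scored as sedentary.* That would follow if the categories were built on raw daily totals, but not if they were built on averages that already omit days below 100 steps. The SAP does not say which.
- *The step-count result is compromised.* The key secondary endpoint uses 2-week averages with their own missing-day rule and does not use this denominator.

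**Conclusion.** The point holds as a minor one. On its plain wording, SAP 5.4.2 lets a day without Fitbit data lower the percent of active days just as an inactive day does, and no wear definition or missing-day rule corrects this. That such days are included is inferred from an unrestricted denominator; the SAP does not say so explicitly. The by-arm summary therefore cannot separate wear from activity.

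The 7.0 to 9.8 points are an illustration. They rest on an assumed 10-point wear difference between arms and scale in proportion to it; with equal wear the false difference is zero. The consequence is confined to an exploratory description of activity.

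**What to change.** In SAP 5.4.2, define a day with valid Fitbit data, using device or sync information where available so that genuine low-step days are kept. Then report by arm, for each analysis period:

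1. the percent of days in the period with a valid synced Fitbit record;
2. active days (at least 100 steps) as a percent of those valid days.

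The all-days percentage may stay as a third line. State also that the three step-count categories use only days, or 2-week averages, with valid data, and say on which day counting starts.

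The cost is a few lines of SAP text and one extra table row, from data already collected. The downside is that the second percentage will sit nearer 100% and show less spread, and that it describes recorded days only.

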After approximately 10 months, the planned enrollment in this study is not expected to reach the target of 1900 participants by the scheduled end of study enrollment window in the first quarter of 2021. Instead, the final anticipated enrollment may only be in the range of about 400-480 participants. Consequently, a reduction in total sample size of this magnitude will have impact on the statistical power for the assumed effect size as well as for various other plausible effect sizes, shown by the figures below. At 50% statistical power, an effect size of 3.5 points in the KCCQ change score (assuming standard deviation is 18) can be detected with a minimum sample size of 400. For power $\geq 80\%$, the required sample size has to be at least 445 if the expected mean difference in KCCQ-TSS change score over 12 weeks is as high as 4.8, assuming the pooled standard deviation is 18. An effect size of this magnitude for the KCCQ-TSS change score was reported in the recently concluded DEFINE-HF study¹⁷. Robust improvements over baseline were also reported for additional KCCQ domains in this study as well as in the SOLOIST study^{17,18}.

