5.1.1. Level of Significance

A 5% level of significance will be used for all analyses. All statistical tests and 95% confidence intervals presented in the analyses of endpoints will be 2-sided.

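### SAP 5.4.2 tests step count against baseline characteristics only in three unordered activity bands, which probably costs power in an exploratory analysis

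*SAP*

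**What the plan says.** SAP 5.4.2 (daily activity bullet) defines three activity levels: below 3000 steps per day, 3000 to 5999, and 6000 or more. It then says that "Associations between daily step count (categorized into activity levels) and baseline characteristics", with age, sex, race, T2DM status and EF type as examples, "will be examined using a 1-way ANOVA for continuous data values and the Fisher exact test for categorical data". No continuous-scale version of this analysis is planned, and no source or reason is given for the 3000 and 6000 cut points.

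The continuous quantity already exists. SAP 2.1 says "Fitbit daily activity data will be aggregated into averages over 2-week intervals", and SAP 5.1.2 and 5.3.1 derive 14-day averages for each participant. Step count also stays continuous elsewhere. The first key secondary endpoint is analysed as change in 14-day average, by MMRM and t-test (SAP 5.3.3), and the next bullet of SAP 5.4.2 correlates total step counts with clinical events.

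On error control, SAP 5.1.1 says "A 5% level of significance will be used for all analyses", and SAP 5.4.2 closes with "No adjustment for multiplicity will be performed for the exploratory analyses listed above".

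**The concern.** Two things are given up. First, banding discards the variation within a band: participants averaging 3,010 and 5,990 steps count as the same, while those at 2,990 and 3,010 count as different. Second, the 1-way ANOVA (a 2-df test when a characteristic such as age is compared across three bands) and the Fisher exact test treat ordered bands as unordered labels.

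At stake is whether modest associations of activity with age, diabetes or EF type are found. SAP 1.4 now expects that "the final anticipated enrollment may only be in the range of about 400-480 participants", against 1,900 planned, so there is little power to spare.

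**Working it through.** **Plan's own figure.** There is none for this analysis. The power statements in SAP 1.4 concern the KCCQ-TSS comparison and are not used here.

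**Inputs from the SAP.** Cut points 3000 and 6000 (5.4.2); two-sided 5% (5.1.1); no multiplicity adjustment (5.4.2); N of 400-480 (1.4).

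**Inputs assumed, because the documents do not give them.** One average step count per participant; mean 2,500-7,000 and SD 1,500-3,000, normal or lognormal; a linear association of correlation r with the (transformed) step count; r set so that the continuous test has a chosen reference power.

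**ANOVA, closed form.**
- Continuous test: noncentral F with 1 and N-2 df, noncentrality N r²/(1-r²).
- Banded test: band k holds a share p_k of participants and has mean m_k on the standard normal scale. The bands keep a fraction R = Σ p_k m_k² of r². With η² = R r², the test is noncentral F with 2 and N-3 df, noncentrality N η²/(1-η²).

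**Worked case: N = 445, shares 0.23/0.55/0.22.**
1. 80% power on the continuous scale needs r = 0.132, noncentrality 7.88.
2. Band means are -1.320, 0.014 and 1.346. R = 0.23×1.320² + 0.55×0.014² + 0.22×1.346² = 0.80.
3. Noncentrality falls to 6.28. Power on 2 df is 60.2%, a loss of 19.8 points.
4. A 1-df trend test on the same bands has 70.6% power, a loss of 9.4 points. So 9.4 points come from banding and 10.4 from ignoring order.

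**ANOVA loss in points, N = 445, by band shares and reference power.**

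| Shares (low/mid/high) | 30% | 50% | 80% | 90% | 95% | 99% |
|---|---|---|---|---|---|---|
| 0.27/0.46/0.27 | 10.7 | 16.9 | 19.2 | 15.7 | 11.7 | 5.0 |
| 0.23/0.55/0.22 | 10.9 | 17.3 | 19.8 | 16.3 | 12.3 | 5.3 |
| 0.50/0.40/0.10 | 11.8 | 19.1 | 22.7 | 19.3 | 14.9 | 6.9 |
| 0.09/0.28/0.63 | 13.1 | 21.5 | 26.9 | 23.6 | 19.0 | 9.7 |
| 0.73/0.24/0.03 | 14.8 | 25.0 | 33.1 | 30.5 | 25.8 | 14.9 |

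The first three rows are reasonably filled bands. At 80-90% reference power they lose about 16-23 points; the whole table spans about 5-33. At a fixed reference power N hardly matters: at N = 1,900 with nearly the same shares the loss at 80% is 19.6.

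**ANOVA, simulation.** N = 440, lognormal averages with medians 3,000-5,500 and log-SD 0.6-0.8, 3,000 datasets per scenario:

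| r | Continuous | Three-band ANOVA |
|---|---|---|
| 0.10 | 55-56% | 36-38% |
| 0.13 | 77-79% | 57-58% |
| 0.15 | 88-89% | 71-72% |

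The closed form gives 55.7%, 78.4% and 88.8% for the continuous test, in agreement.

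**Categorical characteristics, simulation.** A 2×3 exact test was compared with a t-test on raw step count, for a 50:50 characteristic at N = 400 and a 30:70 characteristic at N = 445. With well-filled bands the loss was about 15-20 points for normal counts and 8-17 for lognormal counts. On lognormal counts the raw-scale t-test itself had only 72-87% power, which narrows the gap. A further check at N = 440 gave 12-22. With most participants in one band the loss was 19-30.

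**The case against.** The strongest reply is that the sign of the effect depends on an unknown relationship. If a characteristic differs by 0.35 SD only below 3,000 steps and is flat above, the three-band ANOVA beats a correlation with log steps: 91% v 81%, 84% v 69%, 64% v 41% and 78% v 58% in four scenarios at N = 440. This stands as a real limit of the recommendation. It needs a step exactly at a planned cut point, however, and the documents give no reason to expect one. For a roughly monotone relation the loss is as computed.

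The second reply is that little depends on this analysis. That also stands. Association with baseline characteristics is not among the exploratory objectives (SAP 1.1) or endpoints (SAP 5.4.1), it has no power target or decision rule, and step count is kept continuous where inference depends on it.

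A reader might infer that weak associations here would undermine the reading of the first key secondary endpoint. The documents do not support that. SAP 5.3.1 plans to characterise step-count change against PRO measures and clinical outcomes, and SAP 5.4.2 gives the baseline-characteristic analysis no such role.

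**Conclusion.** The point holds as a minor improvement. SAP 5.4.2 tests a banded, unordered version of a measure already held on a continuous scale, and offers no rationale for doing so. With a roughly monotone relation, reasonably filled bands and 80-90% power on the continuous scale, the cost is about 16-23 points for the ANOVA and roughly 8-22 for the categorical test. Over wider assumptions the ANOVA loss runs from about 5 to 33 points.

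Two stronger readings go too far. One treats a single loss figure as a property of the plan; the documents supply neither the step-count distribution nor the size of any association. The other holds that associations would be missed because of banding alone; a trend test on the same well-filled bands loses only about 7-12 points, so about half of the ANOVA loss comes from the unordered test. Primary and key secondary inference are unaffected.

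**What to change.** In SAP 5.4.2, base the association analysis on each participant's average daily step count as a continuous variable, log-transformed if skewed, and name the 14-day interval used. Use linear regression on each baseline characteristic, or Spearman correlation for continuous and Wilcoxon tests for binary characteristics. Keep the three activity bands for descriptive tables.

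The cost is SAP wording only; no new data are needed. There are two small downsides: the p-values will no longer map onto the banded table, and a sharp threshold exactly at a cut point would be detected less well.
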